### **6.2.9 WEEK 38 PHONE CALL**

- Review concomitant medications and adverse events

### **6.2.10 WEEK 48 ( $\pm$ 7 DAYS)**

The following study evaluations will be performed at Week 48:

- Targeted physical assessment
- Vital signs
- Review of concomitant medications and adverse events
- Socio-Behavioral Assessment; including self-reported smoking history, self-reported exposure to second-hand smoke, self-reported alcohol intake history, contraceptive history
- Urine pregnancy test
- Whole blood and serum for immunologic assay including miRNA profile
- Cervical cytology and ThinPrep® for cervical HPV type
  - Collect menstrual cycle status and recent gynecologic history
- OP oral rinse, vulvar, vaginal and intra-anal swabs
- Vulvoscopy

- Vulvar lesion photography (pre-and post biosy), and quantitative measurement (pre-biopsy) of the qualifying lesion(s)
- Vulvar biopsy or wide excision as per Investigator discretion:
  - All biopsy samples must be sent to the PAC for review

#### **6.2.11 WEEK 52 (± 14 DAYS)**

Subjects will have a Week 52 consultation to discuss their biopsy results and treatment plan. The following assessments will also be performed:

- Review of concomitant medications and adverse events
- Targeted physical assessment
- Vital signs
- Patient Reported Outcomes
- Urine pregnancy test (for subjects receiving a 5th dose only)

Subjects receiving a 5th dose will have the following evaluations performed at Week 52 **after study treatment:**

- Post-treatment AEs including injection site reaction assessment within 30-45 minutes after study treatment
- Distribute Participant Diary

Download EP data from device

#### **6.2.12 WEEK 74 (± 14 DAYS)**

The following study evaluations will be performed at Week 74:

- Review of concomitant medications and adverse events
- Review Week 52 Participant Diary for subjects receiving a 5th dose
- Targeted physical assessment
- Vital signs
- Patient Reported Outcomes
- Urine pregnancy test
- Whole blood and serum for immunologic assay
- OP oral rinse, vulvar, vaginal and intra-anal swabs
- Cervical colposcopy (for subjects ending the study at Week 78 per Amendment 5.0)
- Vulvoscopy

- Vulvar lesion photography (pre-and post biosy), and quantitative measurement (pre-biopsy) of the qualifying lesion(s)
- Vulvar biopsy or wide excision as per Investigator discretion:
  - All biopsy samples must be sent to the PAC for review

### **6.2.13 WEEK 78 (± 14 DAYS)**

Subjects will have a Week 78 consultation to discuss their biopsy results and treatment plan. This will be the final visit for subjects reaching this timepoint under Amendment 5.0, and may occur via phone. The following assessments will also be performed:

- Review of concomitant medications and adverse events
- Targeted physical assessment (or full physical exam for subjects completing the study in-person at Week 78)
- Vital signs (for in-person visit only)
- Urine pregnancy test (for subjects receiving a 6th dose prior to Amendment 5.0 only)
- Socio-behavioral evaluation (for subjects completing the study at Week 78 per Amendment 5.0)

Subjects receiving a 6th dose will have the following evaluations performed at Week 78 **after study treatment:**

- Post-treatment AEs including injection site reaction assessment within 30-45 minutes after study treatment
- Distribute Participant Diary

Download EP data from device

### **6.2.14 WEEK 96 (± 14 DAYS)**

The following study evaluations will be performed at Week 96 for subjects who have reached this timepoint before Amendment 5.0, or for whom this will be the final visit:

- Review of concomitant medications and adverse events
- Review Week 78 Participant Diary for subjects receiving a 6th dose prior to Amendment 5.0
- Targeted physical assessment (or full exam for subjects completing the study at Week 96)
- Vital signs
- Patient Reported Outcomes

- Socio-behavioral evaluation (for subjects completing the study at Week 96 per Amendment 5.0)
- Urine pregnancy test
- Whole blood and serum for immunologic assay
- Cervical colposcopy
  - Photographs during colposcopic examinations of the vagina and/or cervical areas should be obtained if lesions are identified.
- Cervical cytology and ThinPrep® for HPV type
  - Collect menstrual cycle status and recent gynecologic history
- OP oral rinse, vulvar, vaginal and intra-anal swabsVulvoscopy
- Vulvar lesion photography of the qualifying lesion(s)
- Vulvar biopsy or wide excision as per Investigator discretion:
  - All biopsy samples must be sent to the PAC for review

#### **6.2.15 WEEK 100 (± 14 DAYS)**

The following study evaluations will be performed at Week 100 for subjects who have reached this timepoint before Amendment 5.0 or for whom this will be the final visit:

- Review of concomitant medications and adverse events
- Socio-Behavioral Assessment; including self-reported smoking history, self-reported exposure to second-hand smoke, self-reported alcohol intake history, contraceptive history
- Full physical assessment
- Vital signs
- Urine pregnancy test

### **6.3 EVALUATIONS AND PROCEDURES**

#### **6.3.1 INFORMED CONSENT**

All subjects must sign the informed consent prior to any study related procedures being performed (i.e., prior to any screening activities). The informed consent documentation must be in accordance with applicable regulations and GCP. Qualified study personnel will meet with prospective study subjects, explain the study, and provide them with an informed consent form (ICF) that describes the screening tests, eligibility criteria for entering the study, study treatments and follow-up procedures, in a language understandable to the subject. Explanation of the study includes, but is not limited to, study objectives, potential benefits and risks, discomforts/inconveniences, and the subject's rights and responsibilities. The subject is then requested to sign and date the ICF. A copy of the signed informed consent documentation must be provided to the

subject. The qualified study personnel will document the process of obtaining informed consent within the source record. Signed ICFs are maintained in the subject's source records and must be accessible for verification at any time.

### **6.3.2 RESCREENING OF SCREEN FAILURES**

Subjects who sign the informed consent and are assigned a subject identification number (SID) but do not meet the eligibility criteria or fall outside of the screening window will be considered screen failures. If the Investigator believes rescreening is warranted, the Investigator must contact the medical monitor to discuss.

### **6.3.3 ASSIGNMENT OF SUBJECT IDENTIFICATION NUMBERS**

Each subject who consents will be assigned a unique SID, which identifies the subject for all study-related procedures. SIDs are a combination of a up to two alpha letters study code, two alpha letter Country code, two digit site number, plus 3-digit subject number starting with 001 (e.g., VNUS01001). Once assigned, SIDs cannot be reused for any reason. Information regarding the SID and screen date must be documented on a Screening log/system and in the Interactive Response Technology (IXRS).

Subjects meeting eligibility criteria will be randomized by a computer generated allocation schedule.

### **6.3.4 SAFETY EVALUATIONS**

#### **6.3.4.1 PHYSICAL EXAMINATION**

A full physical examination (PE) will be conducted during screening and study discharge unless otherwise indicated. It will include an assessment of the following: general appearance, skin, head, eyes, ears, nose, and throat, and lymph nodes, and respiratory, cardiovascular, gastrointestinal, genitourinary, musculoskeletal, and neurological systems. All assessments not completed should be marked as not done.

A targeted physical assessment will be performed at other visits as determined by the Investigator or directed per subject complaints.

#### **6.3.4.2 VITAL SIGNS**

Vital signs will be measured at specified visits and will include:

- Sitting systolic and diastolic blood pressures with subject sitting at rest for at least 5 minutes before measurement
- Respiration rate
- Heart rate
- Oral temperature measured with an automated thermometer

#### **6.3.4.3 WEIGHT AND HEIGHT**

Weight will be measured at all dosing visits and at screening, and height will be measured at screening to assess BMI.

#### **6.3.4.4 MEDICAL HISTORY**

Medical history, including smoking history and gynecologic history, will be obtained at screening. All relevant (as judged by the Investigator) past and present conditions, as well as prior surgical procedures will be recorded for the main body systems.

#### **6.3.4.5 SOCIO-BEHAVIORAL ASSESSMENT**

Socio-Behavioral Assessment, including self-reported smoking history, self-reported history of exposure to second-hand smoke, self-reported alcohol intake history, self-reported recreational drug use history, self-reported history of contraceptive use and type of contraceptive if known, reproductive history, history of prior cervical dysplasia, and pregnancy history will be obtained at Screening.

At Weeks 48 and 100, socio-behavioral assessment will be performed to document any change from screening. Subjects who complete the study before Week 100 per Amendment 5.0, will have a socio-behavioral assessment completed at their final discharge visit

#### **6.3.4.6 LABORATORY EVALUATIONS**

At screening, blood samples will be taken to be tested for serum chemistry and hematology.

##### Complete blood count (CBC):

- White blood cell (WBC) count with differential
- Red blood cell (RBC) count
- Hemoglobin, Hematocrit
- Platelet count

##### Serum Chemistry:

- Glucose
- Alanine aminotransferase (ALT)
- Blood urea nitrogen (BUN)
- Creatinine
- Electrolytes (Sodium, Potassium, Chloride, Carbon Dioxide or Bicarbonate)
- Creatine Phosphokinase (CPK)

##### Urinalysis (UA):

Urine samples will be tested at screening by dipstick for glucose, protein, and hematuria. If abnormal (presence of protein, hematuria, or glucose  $\geq$  1+) a microscopic examination should be performed.

#### **6.3.4.7 PREGNANCY TESTING**

For subjects of reproductive potential, a negative spot urine pregnancy test is required at screening, and prior to each study treatment, vulvoscopy and surgical excision or biopsy.

#### **6.3.4.8 ELECTROCARDIOGRAM (ECG)**

A single 12-lead ECG will be obtained during Screening after the subject has been in a supine position for 10 to 15 minutes. The ECG should include measurements of ventricular rate, PR, QRS, QRS axis, QT, QTcb or QTcf, ST segment, T wave as well as an Investigator assessment of whether the ECG is normal or abnormal (automated interpretations of ECG should not be used). Abnormal ECGs should be interpreted as "clinically significant (CS)" or "not clinically significant (NCS)" by the Investigator.

#### **6.3.4.9 POST-TREATMENT REACTION ASSESSMENTS**

The PD will capture subject reported local and systemic events for 7 days after the study treatment.

The subject will be provided a PD and will be asked to record the following the evening of study treatment through Day 6:

- Oral temperature and time taken (before 11:59 pm)
- General symptoms of feeling unwell
- Pain and itching at injection site
- Measure redness, swelling, bruising at injection site
- Medications taken

The completed PD will be reviewed with the subject and research staff at 8 -14 Days post-dose.

The study staff will review the PD for general symptoms (e.g. malaise, fatigue, headache, nausea, and myalgia/arthralgia), injection site reaction symptoms (e.g. pain, erythema and edema), medical events and medications. All reported events will be assessed for clinical significance (CS) and reported as adverse event accordingly.

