 Throughout this protocol high grade disease (previously known as VIN2 or VIN3) is referred to as vulvar HSIL according to the 2015 International Society for the Study of Vulvovaginal Disease (ISSVD) Terminology of Vulvar Squamous Intraepithelial Lesions and 2012 consensus recommendation on Lower Anogenital Squamous Terminology (LAST) from the American Society of Colposcopy and Cervical Pathology (ASCCP) and the College of American Pathologists (CAP).

 Inclusive of administration on day of dosing.

 The Version 3.0 protocol amendment halts enrollment of the VGX-3100 with topical imiquimod study group. All subjects who have already been enrolled into the VGX-3100 with imiquimod study group will continue with all study visits per protocol, but no further participants will be enrolled into this group.

 Protocol amendment 5.0 removes Week 96 and 100 from the schedule of events as well as optional dose 6 at Week 78. Data collected on subjects who have already completed these visits and received dose 6 at the time of IRB approval, will be analysed as planned

 No evidence of vulvar HSIL is defined as normal tissue or vulvar LSIL (VIN 1) or condyloma

	tissue samples (i.e. collected via biopsy or excisional treatment) 
Secondary Objectives	Associated Secondary Endpoints
1. Evaluate the safety and tolerability of VGX-3100 delivered IM followed by EP with CELLECTRA™ 2000, alone or in combination with imiquimod	1a. Local and systemic events for 7 days following each dose as noted in the Participant Diary. 1b. All adverse events including SAEs, AESIs, SUSARs, UADEs, and other unexpected AEs for the duration of the study (through Week 100 visit) 
2. Determine the efficacy of four doses of VGX-3100, alone or in combination with imiquimod, as measured by histologic regression of vulvar HSIL	2. Proportion of subjects with no evidence of vulvar HSIL  on histology (i.e. biopsies or excisional treatment) at Week 48 visit
3. Determine the efficacy of four doses of VGX-3100, alone or in combination with imiquimod, as measured by virologic clearance of HPV-16/18 in vulvar tissue	3. Proportion of subjects with no evidence of HPV-16/18  in vulvar tissue samples at Week 48 visit

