#### **1.1.16 POTENTIAL RISKS OF INVESTIGATIONAL PRODUCTS**

Based on the phase 1 and 2 clinical experience, the injection site reactions associated with the IM injection and electroporation are generally mild and limited to a few days in

duration at most. The full risk profile for VGX-3100 is described in the Investigator Brochure.

Local skin and application site reactions are the most frequently reported adverse reactions associated with topical imiquimod 5% treatment. Erythema, erosion, excoriation/flaking, edema, induration, ulceration, scabbing, and vesicles have been reported at the application site [34]. The full risk profile of imiquimod 5% treatment is available in the package insert and prescribing information.

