## 2.2 SECONDARY OBJECTIVES AND ASSOCIATED ENDPOINTS

Secondary Objectives	Associated Secondary Endpoints
1. Evaluate the safety and tolerability of VGX-3100 delivered IM followed by EP with CELLECTRA™ 2000, alone or in combination with imiquimod	1a. Local and systemic events for 7 days following each dose as noted in the Participant Diary. 1b. All adverse events including SAEs, AESI's, SUSARs, UADEs, and other unexpected AEs for the duration of the study (through Week 100 visit) 
2. Determine the efficacy of four doses of VGX-3100, alone or in combination with imiquimod, as measured by histologic regression of vulvar HSIL	2. Proportion of subjects with no evidence of vulvar HSIL  on histology (i.e. biopsies or excisional treatment) at Week 48 visit
3. Determine the efficacy of four doses of VGX-3100, alone or in combination with imiquimod, as measured by virologic clearance of HPV-16/18 in vulvar tissue	3. Proportion of subjects with no evidence of HPV-16/18  in vulvar tissue samples at Week 48 visit
4. Determine the efficacy of VGX-3100 , alone or in combination with imiquimod, as measured by histologic regression of vulvar HSIL to normal tissue	4. Proportion of subjects with no evidence of vulvar HSIL, no evidence of vulvar LSIL (VIN1), and no evidence of condyloma on histology (i.e. biopsies or excisional treatment) at the Week 48 visit
5. Determine the efficacy of four doses of VGX-3100 , alone or in combination with imiquimod, as measured by non-progression of vulvar HSIL to vulvar cancer as determined by histology	5. Proportion of subjects with no progression  of vulvar HSIL to vulvar cancer from baseline to Week 48 visit
6. Determine the efficacy of VGX-3100, alone or in combination with imiquimod, as measured by reduction in the surface area of the qualifying  vulvar lesion(s)	6. Percent reduction in the cumulative surface area of the acetowhite vulvar lesion(s) as determined by the quantitative analysis of standardized pre-biopsy photographic imaging of the qualifying lesion (s) at Week 48 compared to baseline  . Results will be classified as: no clinically significant lesion resolution (reduction in lesion size of 0-25%), partial lesion area resolution (>25% and <100% reduction), and complete lesion resolution (no visible lesion).

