## 7. EVALUATION OF SAFETY AND MANAGEMENT OF TOXICITY

### 7.1 SAFETY PARAMETERS

#### 7.1.1 ADVERSE EVENTS

An adverse event (AE) is defined as any unfavorable and unintended change in the structure, function, or chemistry of the body, or worsening of a pre-existing condition, temporally associated with the use of a product whether or not considered related to the use of the product. In this study, such changes will be monitored, classified, and summarized, as Clinical or Laboratory AEs. Medical condition/diseases present before starting the investigational drug will be considered adverse events only if they worsen after starting study treatment. Throughout the course of the study, all solicited and unsolicited AEs will be monitored and reported on an AE CRF, including the event's seriousness, severity, action taken, and relationship to investigational product(s). AEs should be followed until resolution or stable and the outcome will be documented on the appropriate CRF. All AEs should be recorded in standard medical terminology rather than the subject's own words.

AEs include the following:

- Pre- or post-treatment complications that occur as a result of protocol mandated procedure during or after screening (before the administration of study drug).
- Any pre-existing condition that increases in severity, or changes in nature during or as a consequence of the study drug phase of a human clinical trial, will also be considered an AE.
- Complications of pregnancy (e.g., spontaneous abortion, miscarriage, ectopic pregnancy, fetal demise, still birth, congenital anomaly of fetus/newborn); see [Section 7.1.11](#) for additional information.
- AEs that occur from the study screening visit onwards and throughout the duration of the study, including the follow-up off study drug period will be recorded as an AE.
- Conditions that lead to a medical or surgical procedure.

AEs do not include the following:

- Medical or surgical procedures (e.g., surgery, endoscopy, tooth extraction, transfusion) performed as a result of an AE.
- Pre-existing diseases or conditions or laboratory abnormalities present or detected before the screening visit that do not worsen.
- Situations where an untoward medical occurrence has not occurred (e.g., hospitalization for elective surgery, social and/or convenience admissions).
- Overdose without clinical sequelae.

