### **8.11 SAFETY ANALYSES**

All AEs will be summarized among the safety population by frequency per treatment arm. These frequencies will be presented overall and separately by dose, and will depict overall, by system organ class and by preferred term, the percentage of subjects affected. Additional frequencies will be presented with respect to maximum severity and to strongest relationship to Study Treatment. Multiple occurrences of the same AE will be counted only once following a worst-case approach with respect to severity and relationship to Study Treatment. All serious AEs will also be summarized as above.

The main summary of safety data will be based on events occurring within 14 days of any dose. For this summary, the frequency of preferred term events will be summarized with percentages and exact Clopper-Pearson 95% confidence intervals. Separate summaries will be based on events occurring within 7 days of any dose and regardless of when they occurred.

Any AEs with a missing or partial onset date will be included in the overall AEs, but not be included within specified day-range summaries. AE duration will be calculated as (Stop Date – Start Date) + 1.

Measurements for vital signs as well as changes from baseline will be summarized with descriptive statistics: mean standard deviation, minimum, median, and maximum values by time point and treatment arm, for the mITT population. Baseline is defined as the last measurement prior to the first treatment administration.

The percentage of subjects with abnormal physical examination findings at each time point will be summarized by treatment study group and by body system, for the mITT population.

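### Section 6.3.4.9 ties adverse-event reporting of diary reactions to an undefined clinical-significance judgement, against 6.6, 7.1.1 and 7.4.1; where sites follow it, the result for secondary endpoint 1a can be biased low

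*Protocol*

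**What the plan says.** All references are to protocol Version 5.0.

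Secondary safety endpoint 1a, in the synopsis and again in Section 2.2, is "Local and systemic events for 7 days following each dose as noted in the Participant Diary".

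Section 6.3.4.9 describes the diary and its review by study staff. It ends with the rule for turning entries into AEs: "All reported events will be assessed for clinical significance (CS) and reported as adverse event accordingly". No criteria for clinical significance are given for diary symptoms.

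Section 7.1.1 says that "all solicited and unsolicited AEs will be monitored and reported on an AE CRF". Section 7.4.1 likewise requires solicited and unsolicited AEs to be entered in the electronic data capture system. Section 6.6 calls what the women write in the diary local and systemic AEs. None of these three sections makes recording depend on clinical significance.

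Section 8.11 begins: "All AEs will be summarized among the safety population by frequency per treatment arm". The frequencies are given overall and by dose, by system organ class and preferred term, and by maximum severity. On windows it says "The main summary of safety data will be based on events occurring within 14 days of any dose", with exact Clopper-Pearson intervals for that summary, and then "Separate summaries will be based on events occurring within 7 days of any dose and regardless of when they occurred". It does not name the diary as a data source.

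**The concern.** Endpoint 1a is defined by what the women recorded. The tables that would report it are built from AEs. Whether the two agree depends on the rule that carries a diary entry into the AE data, and the protocol states that rule in two incompatible ways.

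Under 6.3.4.9 the reported reaction rate depends partly on a judgement made separately at about 20 open-label sites without a common threshold. Reactions can be lost but not added, so any bias from this source is downward. The exact interval in 8.11 would then describe the filtered rate and would not show the loss.

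The expected reactions are ones for which the judgement could go either way. Section 1.1.16 describes the injection site reactions associated "with the IM injection and electroporation are generally mild and limited to a few days in" duration. Tolerability of the drug-device combination is a named secondary objective, so the rule for counting these events should not be left open.

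**Working it through.** The plan gives no figure to reproduce, so the main check sets the sections side by side.

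1. **Capture rule A (6.3.4.9).** Diary event → judged for clinical significance → reported as an AE according to the result. The protocol uses clinical significance in the same sorting way for abnormal ECGs (6.3.4.8) and as one of the criteria for recording a laboratory abnormality as an AE (7.1.9). Reading it as a gate is therefore natural, though the sentence does not state outright that other events go unreported.
2. **Capture rule B (6.6, 7.1.1, 7.4.1).** Diary entries are AEs, and all solicited AEs go on the AE form and into the database. There is no gate.
3. **Test case.** A woman records mild injection-site pain (Grade 1 in Table 11) and the site judges it not clinically significant. Under A, read as a gate, it is not an AE. Under B it is. A site cannot follow both.
4. **Consequence for the analysis (8.11).** The 7-day summary has the same window as endpoint 1a, but it counts AEs. Under B it contains the diary reactions. Under A it contains only those that passed the judgement.

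**Illustration of possible size; all rates are assumptions.** Take n = 24, the planned VGX-3100-alone group (Section 3). Let x be the number of women with at least one diary reaction in the 7-day window, and k the share of those women with at least one reaction kept as an AE. Then y = x·k, rounded to a whole woman, and the reported rate is y/n. The exact 95% limits are the 0.025 quantile of Beta(y, n − y + 1) and the 0.975 quantile of Beta(y + 1, n − y).

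| x | k = 1 | k = 0.75 | k = 0.50 | k = 0.25 |
|---|---|---|---|---|
| 12 | 12/24 = 50% (29–71%) | 9/24 = 37.5% (19–59%) | 6/24 = 25% (10–47%) | 3/24 = 12.5% (3–32%) |
| 18 | 18/24 = 75% (53–90%) | 14/24 = 58% (37–78%) | 9/24 = 37.5% (19–59%) | 4/24 = 17% (5–37%) |
| 22 | 22/24 = 92% (73–99%) | 16/24 = 67% (45–84%) | 11/24 = 46% (26–67%) | 6/24 = 25% (10–47%) |

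The column k = 1 is what 7.1.1 and 7.4.1 require, and there the bias is nil. The other columns show what a gate could do. The documents do not say which column applies.

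**The case against.** The case on the other side is substantial. The sentence in 6.3.4.9 does not say that events judged not significant are dropped, and most other text favours capture. Besides 6.6, 7.1.1 and 7.4.1, Section 7.3 says administration site reactions and complaints will be documented. Section 7.2 lists subject-reported symptoms as an AE source without any significance condition, which it attaches only to evaluations and examinations. A site reading the whole protocol might well record everything. This stands, and it makes the defect a contradiction between sections, not a uniform rule that discards events.

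Three stronger readings are tempting, and the documents do not support them.

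- *A reader might infer that endpoint 1a has no analysis at all.* Section 8.11 plans AE frequencies by dose and maximum severity and a separate summary in the same 7-day window. A table built from the diary may also be in the statistical analysis plan, which is not shown.
- *A reader might infer that the staff check at 30–45 minutes is never analysed.* The visit lists in Section 6.2 place that injection-site assessment under post-treatment AEs, and 7.1.7 covers its grading within AE severity, so it enters the AE tables.
- *A reader might infer that mild reactions are in fact under-reported.* Nothing equates mild with not clinically significant, and Table 11 has a mild grade. Under-reporting is a risk that depends on which rule a site follows.

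The possibility of a diary table in the analysis plan does not remove the point. Section 6.3.4.9 instructs sites on what to report, and an analysis plan cannot reconcile conflicting site instructions.

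**Conclusion.** The point holds in a limited form. Section 6.3.4.9 conflicts with 6.6, 7.1.1 and 7.4.1 on whether a diary reaction judged not clinically significant is recorded as an AE. Because 8.11 counts reactions only as AEs, the result for endpoint 1a can be biased low where sites follow 6.3.4.9.

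The size cannot be derived from the documents. It is zero if sites follow 7.1.1 and 7.4.1. Under the assumed rates above it ranges from nothing to a fall from 92% to 25%; these figures show scale and are not estimates. The conclusion rests on reading the 6.3.4.9 sentence as making AE reporting depend on the judgement, which is its natural sense but not its only one. The primary efficacy endpoint is not affected. The change should be made, because the conflict concerns a named secondary endpoint and is cheap to remove.

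**What to change.** - **Section 6.3.4.9:** reconcile it with 6.6, 7.1.1 and 7.4.1. Every local and systemic reaction solicited by the diary is captured as a solicited event with its grade, on the scale that 7.1.7 already assigns, whatever its clinical significance. Keep the clinical-significance judgement as a separate field.
- **Section 8.11:** state that endpoint 1a is summarised from the diary-solicited events, by arm, dose and maximum grade over the 7 diary days, with exact Clopper-Pearson 95% confidence intervals. Use the women who received that dose as the denominator.

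The cost is protocol wording and one extra table. The diary is already completed and reviewed, so no new procedure is needed; any entries that sites left out of the database would have to be entered from the diary. The downside is that reported reaction rates may be higher. No dose or clinical-management rule changes.
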